4.5.2. Immunogenicity Variables

Cellular immunogenicity data will be reported by the Baylor College of Medicine. These data will include the frequency of influenza-specific T cells as measured by fluorescence-based flow cytometric assays. The lab at Baylor will also report the percentage of influenza-specific T cells expressing discrete memory markers (CCR7, CD45RO, and CD57), the percentage of CD4 and CD8 T cells expressing perforin, CD107a, IFN- γ , TNF- α , and IL2, alone or in combination, the percentage of CD4+ T cell subsets expressing IL-4 or IL-17, T follicular helper (TFH) cells (CD4+, CXCR5+, PD-1+, IL-21+) , T follicular regulatory (Tfr) cells (CXCR5+, PD-1+, CD25+, CD127+) , and T regulatory cells (Tregs) (CD25+, Foxp3+)as measured by flow cytometry.

Individual HAI and Neut antibody results will be reported for the IIV4 vaccine strain by the central immunology laboratory at St Louis University. Assay results are reported as a reciprocal titer with values of $10*2^k$, where k=0, 1, 2, etc. The lower limit of detection for both the HAI and Neut assays is 1:10; values below the limit of detection are reported as '<10', and for analysis are imputed as one-half the limit of detection (10/2 = 5). For analysis, the geometric mean of repeated results for each sample will be computed and used as the response for all subsequent calculations. The variation arising from multiple measurements for an individual at a single time point will not be used in subsequent calculations. See Section 3.3 for definitions of derived variables for the analysis of HAI and Neut data.

Assays to determine serum levels of antibodies to M-001 will be performed by BiondVax.

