6.5. Missing Data

All attempts will be made to collect all data per protocol. As missing data are expected to be minimal, no imputation will be performed for missing values. Any data point that appears to be erroneous or inexplicable based on clinical judgement will be investigated as a possible outlier. If data points are identified as outliers, sensitivity analyses will be performed to examine the impact of including or excluding the outliers. Any substantive differences in these analyses will be reported.

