8.1. Primary Immunogenicity Analysis

The primary immunogenicity objective is to determine whether priming with M-001 improves T cell responses. The cells are sorted via flow cytometry, and the percentages of CD4+ and CD8+ T cells expressing perforin, CD107a, IFN γ , TNF- α , IL-2, or any combination of these are calculated as the number of cells positive for these proteins divided by the total number of T cells counted in each sample. To compare the T cell responses between groups, the following Poisson regression model will be fit for each combination of proteins of interest:

$$log(E(Y|X)/Z)=\beta_0+\beta_1*X,$$

where Y is the number of cells expressing a given combination of proteins, X is an indicator variable for Group A, and Z (the offset) is the total number of T cells in each sample. Wald tests will be performed to evaluate whether there are differences in the expression of T cell subsets between the two study arms. As described in Section 6.8, adjustments for multiple comparisons are not planned.

GMPs of CD4+ and CD8+ T cells expressing each combination of proteins and the corresponding 95% bootstrap confidence intervals will also be presented for each study armTable 22Table 23Table 24Table 25. These will be presented in Table 22, Table 23, Table 24, and Table 25 and summarized visually in boxplots over time in Figure 2, Figure 3, Figure 4, and Figure 5.

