[Implementation Note: Do not include p-value column for Tables 28-31, and only include it for Day 36 for Tables 25-27. Include rows for any perforin, any CD107a, any IFN- γ , any TNF- α , and any IL2.]

- Table 23: Geometric Mean Percentage (GMP) of CD8+ T Cell Subsets Expressing Markers Alone or in Combination After M-001 Stimulation with 95% Confidence Intervals by Study Day and Study Arm, Per Protocol Population*
- Table 24: Geometric Mean Percentage (GMP) of CD4+ T Cell Subsets Expressing Markers Alone or in Combination After M-001 Stimulation with 95% Confidence Intervals by Study Day and Study Arm, Modified Intent-to-Treat Population*
- Table 25: Geometric Mean Percentage (GMP) Of CD8+ T Cell Subsets Expressing Markers Alone or in Combination After M-001 Stimulation with 95% Confidence Intervals by Study Day and Study Arm, Modified Intent-to-Treat Population*
- Table 26: Percentage of CD4+ T Cell Subsets Expressing Markers Alone or in Combination After Seasonal Influenza A Antigen Stimulation with 95% Confidence Intervals by Study Day and Study Arm, Per Protocol Population
- Table 27: Percentage of CD8+ T Cell Subsets Expressing Markers Alone or in Combination After Seasonal Influenza A Antigen Stimulation with 95% Confidence Intervals by Study Day and Study Arm, Per Protocol Population
- Table 28: Percentage of CD4+ T Cell Subsets Expressing Markers Alone or in Combination After Pandemic Influenza A Antigen Stimulation with 95% Confidence Intervals by Study Day and Study Arm, Per Protocol Population
- Table 29: Percentage of CD8+ T Cell Subsets Expressing Markers Alone or in Combination After Pandemic Influenza A Antigen Stimulation with 95% Confidence Intervals by Study Day and Study Arm, Per Protocol Population

^{*}Wald test from Poisson regression used to compare groups.

^{95%} CIs calculated via 10,000 bootstrap samples.

Table 30: Summaries of Hemagglutination Inhibition Antibody Against A/Michigan/45/2015 X-275 (H1N1) by Study Day and Study Arm, Per Protocol Population

	Group A: 1 mg M-001 (N=X)	Group B: Placebo (N=X)
Day 1		
n	x	X
GMT (95% CI)	xxx.x(xxx.x,xxx.x)	xxx.x(xxx.x,xxx.x)
Titer ≥ 1:40 - %(95% CI)	x.x (x.x, x.x)	x.x (x.x, x.x)
Day 22		
n	x	X
GMT (95% CI)	xxx.x(xxx.x,xxx.x)	xxx.x(xxx.x,xxx.x)
Seroconversion - %(95% CI)	x.x (x.x, x.x)	x.x (x.x, x.x)
Titer ≥ 1:40 - %(95% CI)	x.x (x.x, x.x)	x.x(x.x, x.x)
Day 43		
n	x	X
GMT (95% CI)	xxx.x(xxx.x,xxx.x)	xxx.x(xxx.x,xxx.x)
Seroconversion - %(95% CI)	x.x (x.x, x.x)	x.x(x.x, x.x)

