16.2.6 Individual Immunogenicity Response Data

Listing 8: 16.2.6.1 Individual Immunogenicity Response Data – Hemagglutination Inhibition against A/H1N1

Study Arm	Subject ID	Planned Study Day	Actual Study Day	Titer

Listings with similar format:

Listing 9: 16.2.6.2 Individual Immunogenicity Response Data – Hemagglutination Inhibition against A/H3N2

Listing 10: 16.2.6.3 Individual Immunogenicity Response Data – Hemagglutination Inhibition against B/Colorado/6/2017

Listing 11: 16.2.6.4 Individual Immunogenicity Response Data – Hemagglutination Inhibition against B/Phuket/3073/2013

Listing 12: 16.2.6.5 Individual Immunogenicity Response Data – Neutralizing Antibody against A/H1N1

Listing 13: 16.2.6.6 Individual Immunogenicity Response Data – Neutralizing Antibody against A/H3N2

Listing 14: 16.2.6.7 Individual Immunogenicity Response Data – Neutralizing Antibody against B/Colorado/6/2017

Listing 15: 16.2.6.8 Individual Immunogenicity Response Data – Neutralizing Antibody against B/Phuket/3073/2013

Listing 16: 16.2.6.9 Individual Immunogenicity Response Data – ELISA Antibody against M-001

Listing 17: 16.2.6.10 Individual Immunogenicity Response Data – Flow Cytometry Results

Study Arm	Subject ID	Planned Study Day	Actual Study Day	% Influenza-Specific T Cell Memory Subsets Expressing Discrete Memory Markers	% CD4 T Cells Expressing IL-4 or IL-17	% CD4 T Cells Expressing Tfh Cells	% CD 4 T Cells Expressing Tfr Cells	% CD4 T Cells Expressing Tregs

16.2.6.11 Individual Immunogenicity Response Data – Cell Mediated Immunity Listing 18:

Study Arm	Subject ID	Planned Study Day	Actual Study Day	Stimulus (M-001 Peptides or Influenza A Antigens)	Cell Type (CD4 or CD8)	Cytokine Combination	Percentage T Cells Expressing Combination

Notes: Cytokines are perforin, CD107a, IFN-γ, TNF-α, and IL2. Do not include rows where the percentage expressed is 0.

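### The primary Wald test prints p of about 0.99 in any marker row where one arm has no positive cells, however strong the other arm's response; the SAP needs a rule for such rows

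*SAP*

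**What the plan says.** SAP 8.1 models the log of the expected positive-cell count, relative to total T cells, as an intercept plus an arm effect, "where Y is the number of cells expressing a given combination of proteins, X is an indicator variable for Group A". The offset Z "is the total number of T cells in each sample". For inference, "Wald tests will be performed to evaluate whether there are differences in the expression of T cell subsets between the two study arms". The footnote to Table 22 repeats this: "Wald test from Poisson regression used to compare groups".

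Table 22 lists all 32 exact combinations of five markers. It adds five marginal rows ("Include rows for any perforin, any CD107a" and likewise for the other three markers), giving 37 Day 36 p-values for CD4. Table 23 has the same layout for CD8, so the per-protocol set holds 74, and Tables 24 and 25 repeat them for mITT. SAP section 5 grades p below 0.001, 0.01 and 0.05 as strong, moderate and weak evidence and marks them with stars.

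Nothing in the plan covers an empty arm:

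- The half-limit rule in SAP 4.5.2 ("values below the limit of detection are reported as '<10', and for analysis are imputed as one-half the limit of detection") is stated for HAI and Neut titers only.
- SAP 6.5 ("no imputation will be performed for missing values") concerns missing values, not observed zeros.
- SAP section 12 records the move from a normal approximation to Poisson regression and adds no safeguard.
- The note to Listing 18, "Do not include rows where the percentage expressed is 0", shows that zeros in individual samples are foreseen.

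**The concern.** The primary immunogenicity question is whether M-001 priming improves T cell responses, and the comparator is saline. A functional subset seen in many M-001 recipients and in no placebo recipient is one of the patterns the primary table should be able to show. The Wald test cannot flag it: as the placebo total reaches zero, the statistic falls to zero instead of rising.

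The neighbouring columns would not warn the reader. SAP 3.3 defines the GMP as the Nth root of a product of percentages, so one subject at zero makes the arm's GMP zero. A row with 20 of 57 M-001 recipients positive and no placebo recipient positive would show a GMP of 0 in both arms, p of about 0.999 and no star.

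**Working it through.** **The plan's own figure.** No stated figure bears on this point. The 80% power in SAP section 5 (2.5-fold, SD 0.75 on the log10 scale, two-sided 0.05) belongs to the superseded t-test. It gives 82.2% at 60 per arm and 80.2% at 57 per arm. I use 57, which is 60 × 0.95 after the SAP's allowance of up to 5% per-protocol exclusions.

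**Why the statistic collapses.** Take equal total offsets in the two arms, S positive cells on M-001, and a fitted placebo total m that the algorithm pushes towards 0. Then

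- estimate = ln(S/m)
- SE = √(1/m + 1/S)
- z = ln(S/m) / √(1/m + 1/S), which tends to 0 as m tends to 0.

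For S = 20:

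| m | estimate | SE | z | p |
|---|---|---|---|---|
| 0.01 | 7.60 | 10.0 | 0.76 | 0.45 |
| 0.0001 | 12.2 | 100 | 0.12 | 0.90 |
| 1e-8 | 21.4 | 10,000 | 0.002 | 0.998 |

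The printed p-value therefore depends on where the software stops.

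**The SAP model fitted with a placebo total of 0** (57 per arm, equal offsets, M-001 cells spread as evenly as possible over subjects). For comparison:

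- exact conditional Poisson p = 2 × (1/2)^S
- likelihood-ratio statistic = 2·S·ln 2 on 1 df
- permutation p, with one cell per positive subject = 2 × C(57,S)/C(114,S).

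| M-001 total | estimate (SE) | Wald p | Likelihood-ratio p | Exact conditional p | Permutation p |
|---|---|---|---|---|---|
| 6 | 22.4 (17,985) | 0.999 | 0.004 | 0.031 | 0.027 |
| 10 | 22.4 (13,931) | 0.999 | 0.0002 | 0.002 | 0.0013 |
| 20 | 23.4 (16,241) | 0.999 | 1.4e-7 | 1.9e-6 | 2.5e-7 |
| 200 | 25.4 (13,961) | 0.999 | 3e-62 | 1.2e-60 | not computed |

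The likelihood-ratio values are asymptotic and too small at 6 to 10 cells. The exact columns are the fair comparison.

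**Cross-checks.**

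- R's Poisson fit at 60 per arm with 120 cells against 0 stops at 21.0 (SE 2,006), z = 0.010, p = 0.992.
- In 500 simulated trials (60 per arm, M-001 mean 2 cells per sample, placebo 0, assumed offsets 20,000 to 200,000), Wald p lay between 0.986 and 0.991. Wald rejected in none of them and the likelihood-ratio test in all.
- If M-001 is the empty arm, p is 0.986.
- A dispersion term does not help: quasi-Poisson p was 0.986 to 0.994 across the fits.

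**How rare a subset must be.** The documents give no value for Z, so this part rests on assumptions. With frequency f, P(placebo total = 0) = exp(−57·Z·f). This is 5% when 57·Z·f = 3, so f = 3/(57·Z):

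- Z = 50,000: f = 1.05e-6
- Z = 500,000: f = 1.05e-7

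In terms of mean positive cells per placebo sample, the chance of an empty arm is 94% at 0.001, 57% at 0.01, 32% at 0.02, 6% at 0.05 and 0.3% at 0.1. If subjects differ with SD 0.75 log10 about those values as medians (60 per arm), it is 77% at 0.001, 11% at 0.01 and practically nil at 0.1.

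**The case against.** The strongest reply is that the trigger is narrow and its occurrence is not shown. It needs zero cells over a whole arm of about 57 samples. The Listing 18 note might be read as evidence that the SAP expects empty arms, but it concerns zero percentages in individual subjects' rows. The M-001 epitopes are described as common to most influenza strains, and previously vaccinated adults are enrolled, so a strong response wholly absent on placebo may be uncommon. All of this stands, and it limits the point to the rarest combinations.

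The size can also be overstated. Six cells against none is only modest evidence (exact p about 0.03), and that assumes six different subjects. With between-subject SD 0.75 log10, six cells fell in a median of five subjects, the median permutation p was 0.057, and about a quarter of runs were below 0.05. If all six come from one subject the permutation p is 1, and a non-significant result is right. With 74 unadjusted tests, 74 × 0.05 = 3.7 would fall below 0.05 by chance under the null. At the SAP's 2.5-fold effect, the chance that placebo is empty while an exact test reaches 0.05 peaks at about 5% per row under simple Poisson. It rises to about 12% at 4-fold and 36% at 10-fold. These points stand too, but they do not rescue the 10-, 20- and 200-cell rows.

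A reader might infer that nearly empty arms fail in the same way. They do not. For 15 cells against 1, z = ln 15/√(1 + 1/15) = 2.62 and p = 0.009; the exact value is 0.0005. That is a loss of sensitivity, and the row still earns a moderate grade. At 120 against 1, Wald p is 1.9e-6.

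Finally, SAP 6.8 calls these analyses non-confirmatory. That lowers the stakes, but the p-values are still printed and starred as graded evidence.

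**Conclusion.** The point holds in a limited form. Where one arm's total is zero, the rule as written gives a wrong p-value, about 0.99 whatever the other arm shows. This follows from the stated model and test and does not depend on any assumed cell count. It is more than a missing detail, because the SAP names the test and that test cannot work in such a row.

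The frequency of the problem is unknown. Under assumed totals of 50,000 to 500,000 T cells per sample and Poisson variation, it is confined to subsets below about 1e-6 to 1e-7. Those are the rarest five-marker combinations; the five marginal rows should not be affected. The contrasting p-values assume equal offsets and cells spread over different subjects. Clustering in a few subjects makes a subject-level p-value larger.

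Two stronger readings are not supported. One is that the failure invalidates the primary analysis or requires a new test in every row: rows with positive cells in both arms have a finite estimate. The other is that any subset seen only on M-001 is proof of induced immunity: in the six-cell example 51 of 57 recipients have none. The figures concern the model-based Wald test; a sandwich variance is not specified and was not examined.

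**What to change.** In SAP 8.1 and the Table 22 footnote (which carries over to Tables 23 to 25), add a rule for empty arms:

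1. If the total of positive cells is zero in one arm, replace the Wald p-value by a named subject-level exact or permutation test of the arm difference, and mark the row.
2. For those rows, report each arm's total positive cells and the number of subjects with any positive cell, since the GMP cannot show the difference.
3. If both arms are empty, print not estimable in place of a p-value.

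The test should work at subject level. The exact conditional Poisson test used above as a yardstick treats cells as independent, and its p-value would be too small when they cluster within subjects. The rule should be fixed before unblinded results are seen, so that no replacement is chosen after p = 0.999 has appeared.

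The cost is a few lines of SAP text and one extra procedure in the program. The test in the remaining rows need not change for this reason; between-subject overdispersion is a separate matter that this rule does not address.

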11. STATISTICAL CONSIDERATIONS

11.1. Study Hypotheses

The study is not designed to test a specific hypothesis for the primary safety objectives. Nevertheless, this trial represents an important opportunity to extend the M-001 safety base.

The primary immunogenicity objective is to determine whether priming with M-001 improves T cell responses. The hypothesis that will be tested is:

$$H_0: GMP_M/GMP_c = 1 \rightarrow \log_{10}(GMP_M) - \log(GMP_c) = 0$$

$$H_1: GMP_M/GMP_c \neq 1 \rightarrow \log_{10}(GMP_M) - \log(GMP_c) \neq 0$$

Where GMP_M and GMP_c are the geometric mean percentage (GMP) percentage of T cell subsets expressing perforin, CD107a, INF γ , TNF- α , and IL-2 for the M-001 and control (placebo) treatment arms, respectively.

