11.5.4. Cell Mediated Immunity Data

Cellular immunogenicity assays will also be performed to assess if M-001 induces a cellular immune response, or primes for a cellular immune response to IIV4. T cell response will be measured as the percentage of T cell subsets expressing perforin, CD107a, IFN- γ , TNF- α , and IL2, alone or in combination in CD4 or CD8 T cells. For each measure at all time points, the GMP and corresponding 95% confidence interval will be presented. For the primary endpoint of T cell response against M-001 peptides 14 days post dose 2, a t-test will be used to compare GMPs between treatment arms.

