3.3. Study Definitions and Derived Variables

Geometric mean percentages (GMPs) are calculated as the product of the observed percentages raised to the 1/Nth root, where N is the number of observed values.

The baseline value for cellular and humoral immunity will be defined as the value obtained on Day 1 prior to M-001 vaccination.

M-001 antibody response after baseline will be summarized by GMTs and the proportion of subjects achieving seroconversion (defined as a minimum four-fold rise in post-vaccination ELISA antibody titer) at each time point, with corresponding 95% confidence intervals.

For individual subjects, fold rise will be calculated as the ratio of: $\frac{post-vaccination\ titer}{pre-vaccination\ titer}$, where pre-vaccination value is always the result obtained at Day 1, prior to the first M-001 dose.

Seroconversion for HAI and Neut assays is defined as either a pre-vaccination titer < 1:10 and a post-vaccination titer $\ge 1:40$, or a pre-vaccination titer $\ge 1:10$ and a minimum four-fold rise in post-vaccination titer.

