12. SUMMARY OF CHANGES IN THE CONDUCT OF THE STUDY OR PLANNED ANALYSES

After the data format for the primary analysis was confirmed, the planned analysis was changed from what is described in the protocol. Instead of utilizing a normal approximation, a Poisson regression model will be fit to test for differences between study arms, as described in Section 8.1.

Additionally, the modified Intent-to-Treat population will only be used as a sensitivity analysis for the primary objective. Originally it was also planned for secondary and exploratory objectives involving antibody responses, but these will not be done in the interest of conciseness.

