14.2 Efficacy/Immunogenicity Data

Table 22: Geometric Mean Percentage (GMP) of CD4+ T Cell Subsets Expressing Markers Alone or in Combination After M-001 Stimulation with 95% Confidence Intervals by Study Day and Study Arm, Per Protocol Population*

Study	Dowf	CD107:	IFN-	TNF-	11.2	Gro	up A: 1 m	g M-001	(Group B:	Placebo	n realizar
Day	Perforin	CD107a	γ	α	IL2	n	GMP	95% CI	n	GMP	95% CI	p-value ^x
				•		Pri	imary End	lpoint				
Day 36	+	+	+	+	+	х	X.X	x.x, x.x	Х	X.X	X.X, X.X	
	+	+	+	+	-	х	X.X	x.x, x.x	Х	X.X	X.X, X.X	
	+	+	+	-	+	х	X.X	x.x, x.x	Х	X.X	X.X, X.X	
	+	+	+	-	-	х	X.X	x.x, x.x	Х	X.X	X.X, X.X	
	+	+	-	+	+	х	X.X	x.x, x.x	Х	X.X	X.X, X.X	
	+	+	-	+	-	х	X.X	x.x, x.x	Х	X.X	X.X, X.X	
	+	+	-	-	+	х	X.X	x.x, x.x	Х	X.X	X.X, X.X	
	+	+	-	-	-	х	X.X	x.x, x.x	Х	X.X	X.X, X.X	
	+	-	+	+	+	х	X.X	x.x, x.x	Х	X.X	X.X, X.X	
	+	-	+	+	-	х	X.X	x.x, x.x	Х	X.X	X.X, X.X	
	+	-	+	-	+	х	X.X	x.x, x.x	Х	X.X	X.X, X.X	
	+	-	+	-	-	х	X.X	x.x, x.x	Х	X.X	X.X, X.X	
	+	-	-	+	+	х	X.X	x.x, x.x	Х	X.X	X.X, X.X	
	+	-	-	+	-	х	x.x	x.x, x.x	Х	X.X	X.X, X.X	
	+	-	-	-	+	х	X.X	x.x, x.x	Х	X.X	X.X, X.X	
	+	-	-	-	-	х	X.X	x.x, x.x	Х	X.X	X.X, X.X	
	-	+	+	+	+	х	X.X	x.x, x.x	Х	X.X	X.X, X.X	
	-	+	+	+	-	х	X.X	x.x, x.x	Х	X.X	X.X, X.X	
	-	+	+	-	+	х	X.X	x.x, x.x	Х	X.X	X.X, X.X	
	-	+	+	-	-	х	X.X	x.x, x.x	Х	X.X	X.X, X.X	
	-	+	-	+	+	х	X.X	x.x, x.x	Х	X.X	X.X, X.X	
	-	+	-	+	-	х	X.X	x.x, x.x	Х	X.X	X.X, X.X	
	-	+	-	-	+	х	X.X	x.x, x.x	Х	X.X	X.X, X.X	
	-	+	-	-	-	х	X.X	x.x, x.x	Х	X.X	X.X, X.X	
	-	-	+	+	+	х	X.X	x.x, x.x	Х	X.X	X.X, X.X	
	-	-	+	+	-	х	X.X	x.x, x.x	X	X.X	X.X, X.X	
	-	-	+	-	+	х	X.X	x.x, x.x	Х	X.X	X.X, X.X	
	-	-	+	-	-	X	X.X	x.x, x.x	Х	X.X	X.X, X.X	
	-	-	-	+	+	х	X.X	x.x, x.x	Х	X.X	X.X, X.X	
	-	-	-	+	-	х	X.X	x.x, x.x	Х	X.X	X.X, X.X	
	-	-	-	-	+	Х	X.X	x.x, x.x	х	X.X	X.X, X.X	

Study	D. C.	CD107	IFN-	TNF-	11.2	Gro	up A: 1 m	g M-001	(Group B:	Placebo	
Day	Perforin	CD107a	γ	α	IL2	n	GMP	95% CI	n	GMP	95% CI	p-value ^x
	-	-	-	-	-	X	X.X	X.X, X.X	X	X.X	X.X, X.X	
	+	+/-	+/-	+/-	+/-	X	X.X	X.X, X.X	X	X.X	X.X, X.X	
	+/-	+	+/-	+/-	+/-	X	X.X	x.x, x.x	х	X.X	X.X, X.X	
	+/-	+/-	+	+/-	+/-	X	X.X	x.x, x.x	х	X.X	X.X, X.X	
	+/-	+/-	+/-	+	+/-	X	X.X	X.X, X.X	X	X.X	X.X, X.X	
	+/-	+/-	+/-	+/-	+	X	X.X	X.X, X.X	X	X.X	X.X, X.X	

Exploratory Endpoints

Repeat for Baseline, Day 15, Day 43, Day 78, Day 172, Day 186, and Day 200 without p-value column.

Notes: N = number of subjects in Per Protocol population.

Tables with similar format:

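### The primary hypothesis is a GMP ratio, but the plan gives no between-arm ratio with a confidence interval, and the p-value printed beside the GMPs tests a different ratio

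*SAP*

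**What the plan says.** **Protocol.** Section 11.1 sets the null hypothesis as a GMP ratio of 1, equivalently a log10 difference of 0: "Where GMP_M and GMP_c are the geometric mean percentage (GMP) percentage of T cell subsets expressing perforin" and the other markers, by arm. Section 11.5.4 tests it directly: "a t-test will be used to compare GMPs between treatment arms". Section 11.3.4 illustrates power on the same scale, for a GMP fold-change in T cells expressing IFN-γ.

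**SAP definition.** Section 3.3 defines a GMP as a geometric mean of subject percentages, "calculated as the product of the observed percentages raised to the 1/Nth root". Section 3.2.1 keeps the GMP as the primary immunogenicity outcome measure.

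**SAP test.** Section 8.1 fits a Poisson regression of the count of positive cells on an indicator for Group A, with total T cells as offset. Then "Wald tests will be performed to evaluate whether there are differences in the expression of T cell subsets between the two study arms". Section 12 discloses the change: "Instead of utilizing a normal approximation, a Poisson regression model will be fit to test for differences between study arms". It does not say that the tested quantity changes with the test.

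**SAP presentation.** Section 8.1 adds arm-wise GMPs, and "the corresponding 95% bootstrap confidence intervals will also be presented for each study" arm. The Table 22 shell, titled "with 95% Confidence Intervals by Study Day and Study Arm, Per Protocol Population", has n, GMP and 95% CI for each arm and then one p-value column, footnoted "Wald test from Poisson regression used to compare groups". Tables 23-25 share the format. SAP 5 grades evidence by three p-value thresholds, marked with asterisks.

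**The concern.** The Day 36 rows are where a reader will look for the answer to the primary question. They print two GMPs, an interval for each, and a starred p-value. A reader will naturally take the p-value as a test of the two GMPs beside it, which it is not. Nor do the rows give the quantity in the hypothesis, the between-arm GMP ratio, with any measure of its uncertainty. No other section, table, figure or listing plans it, and none plans the exponentiated Poisson coefficient with an interval.

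The analyses are declared non-confirmatory, so the size of the effect and its precision are the main product. Protocol 11.5 says the topline report, which includes Tables 22-25, will serve the planning of later trials, and that use needs a ratio with an interval. By contrast, SAP Table 48 does plan a between-arm difference with a 95% CI for solicited events.

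**Working it through.** **Inputs.** From the documents: 60 per arm; 54 per arm under 10% dropout; up to 5% excluded from the per-protocol analysis (60 × 0.95 = 57 per arm); two-sided alpha 0.05; log10 SD 0.25, 0.50 or 0.75; the 2.5-fold illustration (log10 2.5 = 0.398). Assumed: unequal arm SDs, chosen inside the 0.25-0.75 range of Protocol Table 10, because the documents give no arm-specific SDs.

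**1. The plan's own power figures.** For a two-sample t-test, the noncentrality is 0.398 / (0.75 × √(2/60)) = 0.398 / 0.137 = 2.91. Power is 82.2% at 60 per arm, 80.2% at 57 and 78.0% at 54. The stated 80% is consistent with rounding. Every cell of Protocol Table 10 (SAP Table 5) reproduces within about 1.3 points; for example, 3-fold at SD 0.75 gives 93.3% (stated 93) at 60 per arm and 90.6% (stated 90) at 54. The planning arithmetic is therefore sound, and it is on the GMP-ratio scale.

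**2. What the Poisson test targets.** With one binary covariate and an offset, the fitted coefficient is

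log[(ΣY_A/ΣZ_A) / (ΣY_B/ΣZ_B)],

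the log ratio of pooled positive fractions. Each arm's rate is an arithmetic mean of subject fractions weighted by cells counted. A GMP averages logs, so it is a different summary.

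**3. How far the two targets can differ.** If subject percentages are lognormal and unrelated to the number of cells counted, then

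rate ratio = GMP ratio × exp[(ln 10)² × (SD_A² − SD_B²) / 2], with (ln 10)² = 5.302.

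At a true GMP ratio of 1.0:

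| SD, M-001 | SD, placebo | Rate ratio |
|---|---|---|
| equal | equal | 1.00 |
| 0.60 | 0.50 | 1.34 |
| 0.75 | 0.60 | exp(5.302 × 0.2025 / 2) = 1.71 |
| 0.75 | 0.50 | exp(5.302 × 0.3125 / 2) = 2.29 |

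Exchanging the two SDs inverts the ratio.

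**4. What the arm-wise intervals leave out.** These are t intervals on the log10 scale, as a stand-in for the bootstrap.

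- Ratio interval at 60 per arm, SD 0.75: factor 10^(1.980 × 0.75 × √(2/60)) = 10^0.271 = 1.87. It excludes 1 once the observed ratio exceeds 1.87.
- Arm interval: factor 10^(2.001 × 0.75 / √60) = 10^0.194 = 1.56. Two such intervals separate only at 1.56² = 2.44.

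Observed ratios between 1.87 and 2.44 would thus have a ratio interval excluding 1 while the printed arm intervals still overlap. At SD 0.50 the corresponding range is 1.52 to 1.81. This result needs no assumption of unequal SDs.

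**5. What the added column would show.** For an observed 2.5-fold ratio at 60 per arm, the 95% CI would be 2.03-3.08 (SD 0.25), 1.65-3.79 (SD 0.50) or 1.34-4.67 (SD 0.75). At 54 per arm and SD 0.75 it would be 1.29-4.83.

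**The case against.** Much can be said for the plan as written. The change of test is disclosed in SAP 12 and followed confirmation of the data format. The outcome measure is arm-level GMPs at baseline and Day 36, and Table 22 delivers those. A count model accepts zeros, whereas one zero percentage makes a GMP zero and its log undefined. Zeros are expected: the note to SAP Listing 18 omits zero rows, and Table 22 covers all 32 marker combinations. Moving the p-value back to the log scale is therefore debatable, and this point does not depend on it. A rise in the arithmetic mean without a rise in the GMP could also be a real response to M-001. These arguments stand as reasons to allow a count model. They do not supply the missing interval or make the p-value a test of the GMPs.

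Four stronger readings are tempting, and the documents do not support them:

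- *That the primary table has no effect estimate or no intervals.* It has an interval for each arm, and dividing the two GMPs gives the point ratio. Only the between-arm uncertainty is absent.
- *That the trial was sized on a 2.5-fold ratio.* Protocol 11.3.4 fixes 120 subjects and offers that figure as an illustration for IFN-γ, not as a target for every row.
- *That the p-values and GMPs will conflict.* The targets coincide at equal log-scale SDs under the model in step 3, and the planned power grid uses one SD per scenario.
- *That the Poisson Wald test is shown here to be too liberal.* Extra-Poisson variation between subjects is a separate question, which turns on cell counts and positive fractions the documents do not give. Nothing above relies on it.

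SAP 10 has a rounding rule that mentions regression coefficients, but no primary table shell has a place for one, and the exponentiated coefficient would not be the GMP ratio.

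**Conclusion.** The point holds as a gap in estimation and labelling. The hypothesis and power illustration are on the GMP-ratio scale; the plan reports arm-wise GMPs and a p-value for the ratio of pooled rates, with no between-arm ratio and interval on either scale. This follows from the text and table shells alone.

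Its size has two parts. The missing interval is about times or divided by 1.87 at 60 per arm and SD 0.75, and 1.52 at SD 0.50; the printed arm intervals do not convey it. The mismatch between targets is nil at equal SDs and reaches a rate ratio of 1.7 at a GMP ratio of 1.0 under assumed SDs of 0.75 and 0.60. That second figure shows what is possible and does not predict what will occur. Because the analyses are declared non-confirmatory, this is a recommended correction and does not invalidate the design.

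**What to change.** For the Day 36 rows of Tables 22-25:

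1. Add the GMP ratio (M-001/placebo) with a 95% CI from the 10,000 bootstrap samples already planned, and name it in SAP 8.1 as the estimate for the hypothesis in Protocol 11.1.
2. Prespecify one rule for zero percentages, and apply it to both the ratio and the arm-wise GMPs, which already need it.
3. If the Poisson p-value is kept, print its rate ratio with a 95% CI beside it. State in the footnote and in SAP 12 that it tests a ratio of pooled rates and not the GMP ratio.

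The cost is two to three extra columns, the zero rule and a few sentences of SAP text. No new data or visits are needed. The zero rule is the one real decision, since for rare marker combinations the ratio may depend on it.
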